	Correlation of each type of device with each complication group as a predictor of exacerbation (i.e. determine which device(s) are most useful).	Table of devices / correlations / confidence levels.	October 2020				
Intervention(s)	There are no clinical interventions in this study.						
Comparator	Comparison data wil study.	I be obtained from GP surgeries	participating in the				

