#### 5.2. Method

The study will use patient data held in care home and GP records to identify potential participants. Health professionals working for the participating care homes or GP surgeries will then use inclusion and exclusion criteria to select patients for invitation to join the study. In the care home phase (Phase 1), the care home manager will sign and hand an invitation letter and Patient Information Leaflet to the potential participants whom they have identified and ask them to sign an attached form giving consent to be approached by the research team for informed consent. In Phase 2, the primary care phase, GP surgery staff will send the invitation letter and Patient Information Leaflet to potential participant and process the returned forms, booking informed consent appointments. The research team is seeking the support of the North Thames Clinical Research Network in parallel with the application to the HRA/REC; if successful, staff from the CRN will support the recruitment and consenting process in Phase 2 only.

The study cohort will be taken from those who have needed most urgent care and who have the largest number of comorbidities, as defined by the inclusion and exclusion criteria above.

**Phase 1** of the study will be conducted with up to 100 participants residing in care homes. Either Health Research Assistants employed by the research team or local care home employed professionals (the choice between these two to be at the care home's discretion) will use connected medical devices to collect data from the cohort at twice-weekly intervals for twelve weeks. In this phase **all devices will be used with all participants**.

NHS activity data will be obtained from the records held in GPs' clinical systems at the end of Phase 1 to enable models to be constructed that will test the study hypothesis and allow the mapping of chronic conditions to device types to be optimised. This will mean that in **Phase 2**, participants will only be asked to use devices that have been proved in **Phase 1** to be effective at collecting useful data relevant to their specific set of co-morbidities.

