### 5.5. Rationale for undertaking the study

In 2019 there has been a step change in the costs of personal medical devices, ease of use, cost of connectivity and machine learning capabilities. These changes render the technology more affordable by the NHS and more usable by elderly people. In 2018, the Emergency Care Data Set (ECDS) was introduced to all A&E departments in England and for the first time comprehensive outcomes based data on

Clinical Research Protocol CONFIDENTIAL

L2S2 ltd Page 13 of 38

attendance at A&E departments is available. Together the changes in technology and availability of high-quality reference data make this study possible.

Participants will be selected who are likely to exacerbate during the trial period and therefore the size and duration of the study are considered adequate to test the hypothesis thoroughly.

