#### 6. OBJECTIVES AND OUTCOME MEASURES

Objectives	Outcome Measures	Timepoint(s) of evaluation of this outcome measure (if applicable)
Primary Objective The purpose of the study is to find out the confidence of correlation and its statistical significance	The correlation confidence level for exacerbation prediction from data collected from medical devices in the participant's home or care home with actual attendance data obtained from GP surgeries.	End of study (study is non-interventional)
Secondary Objectives  1. Determine drop out percentage	1. Dropout Percentage: Number of readings taken by patients compared to their agreed plan.	End of study
2. Determine relationship between frailty and ability to adhere to plan	2. Correlation between adherence to agreed plan and the participant's frailty score.	
3. Determine relationship between number of co-morbidities and resource required.		

4. Determine effectiveness of different devices as predictors of exacerbation by complication group.

- 3. Number of visits required for each complication group by number of comorbidities
- 4. Correlation of each type of device for each complication group as a predictor of exacerbation (i.e determine which device(s) are most useful).

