#### 7. STUDY DESIGN

The study type will be observational, collecting data from wearables and remote monitoring medical devices to determine correlations with primary data collected from GP surgeries attended by the participants in the course of the study.

Participants will be recruited by West Essex CCG from patients in their region who meet the study inclusion criteria.

The first phase of research with up to 100 participants will be conducted in care homes with twice-weekly visits from Health Research Assistant's (HRA) employed by the research team, equipped with a standard kit of medical devices who will ensure the devices are used appropriately to maintain data quality and who will monitor the effectiveness of the electronic devices. If care homes would rather be trained to undertake these duties using their own staff, the research team will train them and remunerate the care home for these staff costs.

The second phase of 500 participants will be conducted in participants' homes and care homes with visits from a research team HRA to ensure safe and effective use of condition specific wearable and monitoring devices when this is requested. Visit frequency will be automatically adjusted by feedback from the monitoring systems. (Typically once per week.)

The electronic devices will provide primary medical data as well as metadata regarding battery charging behaviour, adherence to study procedures, effect of active compliance management and direct feedback from the participants. The visit frequency will be adjusted to ensure maximum effectiveness of the equipment and to maximise economic benefit to allow a 'best practice' baseline to be established.

The medical devices issued to each patient will be determined by observations and data collected by the HRAs in conjunction with baseline data derived from GP data.

In **Phase 1**, all devices will be used to take measurements from all participants. Devices will be issued to HRAs who will use them to ensure correct use and valid data.

In **Phase 2**, devices will be allocated to participants based on data gathered in **Phase 1**. It is anticipated that this will demonstrate the best combinations of devices for recording health measurements for different sets of co-morbidities, and prove or disprove the following assumptions:

Clinical Research Protocol L2S2 ltd Page 16 of 38

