### 12.2. Decision points

An interim report will be presented to the CCG based on the data collected from the first 100 patients in the care homes in the middle of May 2020. This will include outcome performance measures on the device / condition groupings, the confidence of correlation between the measurements and the actual data from the A&E departments and the GPs. The decision when to proceed to phase 2 will be made jointly by L2S2 and the CCG.

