## 20.3. Contractual arrangements

Appropriate contractual arrangements will be put in place with all third parties, including but not limited to: hospitals providing baseline and monthly data, GP surgeries providing baseline and monthly data, contract care organisations, any subcontractors.

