## 26. Appendix D NHSD comorbid conditions

The attached spreadsheet lists the Snomed codes for comorbid conditions that will be extracted from Accident and Emergency Department ECDS data. This data together with GP data and the collected data from wearables and appropriate medical devices will be used to build models to test the study hypothesis.

[name], the Chief Investigator for this study was responsible for the design and deployment of the ECDS to all Accident and Emergency Departments in England in 2018 as the national database for emergency medicine.

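### The event source for the primary outcome is inconsistent: GP records only where the outcome is defined, A&E or hospital data added elsewhere

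*Protocol*

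**What the plan says.** **GP records only.** The primary outcome in Section 6 relates predicted exacerbations "with actual attendance data obtained from GP surgeries". The synopsis says that comparison data will "be obtained from GP surgeries". Section 7 collects device data to "determine correlations with primary data collected from GP surgeries attended by the participants in the course of the study". Section 5.2 says of the end of Phase 1 that "NHS activity data will be obtained from the records held in GPs" (the sentence continues to their clinical systems), and it names the participant's GP as the source at the end of Phase 2. Section 13.1, on source data, lists GP clinical systems, the participant app and carer-entered readings. It lists no hospital or A&E feed.

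**A&E or hospital data as well.** Section 12.2 bases the interim report on the first 100 care home patients and on the agreement between their measurements and "the actual data from the A&E departments and the GPs". Section 9.4 justifies using identifiable data by the need to link to hospital as well as GP records. Section 19.6 keeps linkage keys for both. Section 20.3 plans contracts with "hospitals providing baseline and monthly data", alongside the same supply from GP surgeries.

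**The event.** Section 12.1 describes the index condition as deterioration serious enough to need a hospital admission. Section 12.5 describes exacerbations that lead to urgent unscheduled care.

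**The concern.** The source of actual events is the reference standard for the primary outcome: every prediction is scored right or wrong against it. The protocol describes it in two ways, GP data alone and GP data plus A&E or hospital data.

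The conflict is sharpest in Phase 1. Section 5.2 builds the Phase 1 models from GP records, while Section 12.2 reports the same patients against A&E and GP data together. Phase 1 findings decide which devices Phase 2 participants are given (Sections 5.2 and 7), so the choice of source affects more than the final report.

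Many of the events sought would happen in a hospital rather than at the surgery. If some were absent from the GP record, a correct warning would be scored as a false alarm, and an event that the algorithm failed to flag would be scored as a correct negative.

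**Working it through.** **1. The sections side by side.**

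| Section | Event or comparison source |
|---|---|
| Synopsis; 5.2 (both phases); 6; 7; 13.1 | GP only |
| 12.2 (interim report, Phase 1 patients) | A&E and GP |
| 9.4, 19.6 (linkage) | Hospital and GP |
| 20.3 (data supply) | Hospital and GP, baseline and monthly |

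No section ranks the sources, gives a rule for combining them, or says that the GP record holds every A&E attendance or admission with its date.

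**2. Inputs for the size.**
- Sensitivity SN = 0.85, specificity SP = 0.80 and W = 0.05, from Section 12.1.
- Incidence p = 0.35, from the Stage I and II tables in 12.1, with p = 0.55, from the text of 12.1, as an alternative. The tables apply 35% per month; here p is the share of participants with an event in one evaluation window.
- f = share of true events missing from the GP record. The protocol gives no figure, so f is an assumption, shown from 0 to 30%.
- Assumption: whether an event is captured does not depend on whether the algorithm flagged it.

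**3. The plan's own figure first.** Required events = 1.96² × 0.85 × 0.15 / 0.05² = 195.9. Dividing by p = 0.35 gives 559.8, which matches the printed N(SN) of 560.

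**4. Apparent specificity.** Missed events join the apparent non-events. A fraction SN of them carries a flag and counts as false positives; the rest count as true negatives. So

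apparent SP = [(1 − p) × SP + p × f × (1 − SN)] / [(1 − p) + p × f].

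At p = 0.35 and f = 0.10: (0.65 × 0.80 + 0.035 × 0.15) / (0.65 + 0.035) = 0.52525 / 0.685 = 0.767.

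| f (assumed) | Apparent SP, p = 0.35 | Apparent SP, p = 0.55 | Apparent incidence, p = 0.35 | N(SN) at that incidence |
|---|---|---|---|---|
| 0% | 80.0% | 80.0% | 35.0% | 560 |
| 5% | 78.3% | 76.3% | 33.3% | 589 |
| 10% | 76.7% | 72.9% | 31.5% | 622 |
| 20% | 73.7% | 67.2% | 28.0% | 700 |
| 30% | 71.0% | 62.6% | 24.5% | 800 |

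**5. In participants.** With 500 participants and 175 events (the first month of the Stage II table), f = 10% loses 17.5 events. About 14.9 (85%) become false positives and 2.6 (15%) become true negatives. Then 262.6 of 342.5 apparent non-events are true negatives, again 76.7%.

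**6. Sensitivity.** Under the independence assumption it stays at 85%, because the captured events are a random subset of all events.

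**The case against.** The strongest reply is that GP-only collection is a coherent plan. Every section that defines the outcome or its collection says GP, and Section 7.1 has the research team take urgent care attendance history from the GP's clinical system in Phase 2, so the authors evidently regard that record as holding such attendances. The A&E and hospital mentions sit in the interim report, blinding, confidentiality and contract sections, and each names GP data too. This stands in part: the conflict is GP only against GP plus hospital. A reader might infer two rival standards, but the hospital passages add a source and do not replace one. Section 12.2 still changes the source for the Phase 1 patients, and the hospital supply in 20.3 has no stated role in the outcome.

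Some stronger readings are also not supported:
- **Appendix D as evidence.** Its phrase "that will be extracted from Accident and Emergency Department ECDS data" refers to codes for comorbid conditions, not attendances. Section 5.5, where technology changes and "availability of high-quality reference data make this study possible", is rationale and does not designate an outcome source.
- **That the sources do differ in completeness or dates.** The protocol neither says so nor excludes it.
- **That the algorithm would fail.** 85% and 80% are called lowest acceptable values for sizing, but the primary outcome is a correlation confidence level and no pass/fail test on specificity is set.
- **That every missed attendance counts as an error.** Only the flagged ones do.
- **That the phases or sites will use different sources.** Section 5.2 specifies GP data for both phases and nothing varies the source by site; only 12.2 hints at a difference.

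Rules for de-duplication and dating could be left to an SAP. Whether hospital data contribute to the primary outcome could not, because an SAP choosing either way would contradict some sections of this protocol.

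**Conclusion.** The inconsistency is real, concerns the primary outcome, and is established by the protocol's text alone. Its effect on the results is conditional. If GP records miss 5% to 30% of events, apparent specificity falls from 80% to between 78.3% and 71.0% at 35% incidence, or to between 76.3% and 62.6% at 55%. Apparent incidence falls as well, so the sample needed for the planned precision on sensitivity rises, for example from 560 to 622 at 10% missing. These figures rest on an assumed missing share and on capture being independent of the flag. If GP records are complete, there is no bias, and what remains is a contradiction to be cleared up. If capture depends on the flag, sensitivity is biased too, in a direction that the documents do not allow one to state. The point should be settled before outcome data are extracted.

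**What to change.** In Section 6, name one event source for both phases: the hospital and A&E data already planned, together with GP-recorded unscheduled care. State how records from the sources are combined and dated. Taking the union, with the earliest recorded date for each event, is one workable rule, but not the only one.

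Keep the event definition the same as the one used for sizing in 12.1, because adding every GP-recorded unscheduled contact could widen the event and change its incidence. Section 12.1 itself refers both to deterioration needing admission and, more broadly, to episodes needing NHS treatment, so Section 6 should say which is meant.

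Report results from GP records alone as a sensitivity analysis; comparing the two would also show the capture rate that the protocol now lacks. Align the synopsis and Sections 5.2, 7, 12.2 and 13.1.

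The cost is protocol wording plus modest linkage and de-duplication work. The linkage keys (19.6) and the hospital data supply (20.3) are already planned.

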## 3. SYNOPSIS

Clinical Research Protocol L2S2 ltd Page 6 of 38

Study title	Service demand pred	iction based on information from o	connected devices							
Internal ref. no. / short title	Service demand pred	iction based on information from o	connected devices							
Study registration	IRAS Project ID 27614	9 17-11-2019								
Sponsor	[name]	Epping,								
Funder	NHS England, [name].									
Study Design	Clinical investigation	or other study of a medical device								
Study Participants	Patients older than 65 years AND more than 2 comorbid conditions AND / OR more than one requirements for unscheduled urgent care in previous year AND / OR medium or high frailty score									
Sample Size	Phase 1: 100; Phase 2	:: 500								
Planned Study Period		dy period: 11 months rticipation period 24 weeks								
Planned Recruitment period	Phase 1: April/May 2020 Phase 2: July/August 2020									
	Objectives	Outcome Measures	Timepoint(s)							
Primary	To test the hypothesis: If information about patient behaviour, conditions and events, captured from wearables, monitors and other smart technologies	Phase 1: 100 patients:  Optimised models generate dynamic personalised monitoring plan for each participant.  Phase 2: 500 patients:	July 2020							
	can predict demand for services, then, providing these technologies to patients and using the data generated will enable providers to preempt and redirect	Model linking health outcomes to NHS activity will be developed and tested.  Confidence of correlations between measured data and observed data from actual unscheduled care data during study period.	October 2020							

	demand or design new services.						
Secondary	Dropout Percentage: Number of readings taken by patients compared to their agreed plan.	Two percentages. Participants who can / want to receive automated compliance reminders. Participants who cannot / don't want to receive automated compliance reminders.	October 2020				
	Correlation between adherence to agreed plan and the participant's frailty score.	Correlation	October 2020				
	Number of visits required for each complication group by number of comorbid conditions to achieve best value	Table / charts / recommendations with confidence levels	October 2020				

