In **Phase 2**, a total of 500 participants will be enrolled who meet the study inclusion criteria. Any participants from **Phase 1** who want to continue to have their health measurements taken will be permitted to proceed to **Phase 2** and the remained, up to a total of 500, will be recruited from their GP surgeries and asked to participate from their own homes. Continuing care home residents will continue to receive twice-weekly visits from the project's Health Research Assistants (or care home employed

professionals, as appropriate); those participating in the study from their own homes will do so autonomously using the smartphone, the Reassure OneApp application loaded onto the smartphone, and a set of devices appropriate to their co-morbidities. They will be shown how to take their health measurements during an initial visit from one of the project's Health Research Assistants, and the Reassure OneApp application will also display reminders of how to do this. In addition to this, Health Research Assistants will be available to make visits to the participant's home to support them in collecting their health measurements at the request of the participant.

The medical devices will send back data to central server facilities in Cambridge, UK to L2S2's patient management system that will automatically adjust the visit frequency for each patient and prompt compliance to minimise dropout.

At the end of **Phase 2**, NHS activity data will be obtained from the participants' GP to allow correlation between the actual recorded instances of requirement for unscheduled care and the data collected in the trial from the medical devices.

Machine learning and statistical analysis will be used to determine the validity of using home collected and care home collected data from smart medical devices to predict future likelihood of requirements for unscheduled urgent care.

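### The outcome called dropout percentage is an adherence ratio with an unsettled denominator, and the frailty–adherence correlation is not limited to people who take their own readings

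*Protocol*

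**What the plan says.** Section 6 gives as its first secondary objective "Determine drop out percentage", and measures it as "Dropout Percentage: Number of readings taken by patients compared to their agreed plan". The Synopsis (Section 3) repeats the definition and splits the result in two, by whether participants receive automated reminders ("Participants who can / want to receive automated compliance reminders") or do not. It gives no split by who takes the reading.

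The second secondary objective is "Determine relationship between frailty and ability to adhere to plan". Its measure is "Correlation between adherence to agreed plan and the participant's frailty score", with no stated restriction.

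On the plan itself, the Synopsis says "Optimised models generate dynamic personalised monitoring plan for each participant". Section 10.9 lets the returned data determine the spacing of measurements. Section 5.2 says the system will "automatically adjust the visit frequency for each patient and prompt compliance to minimise dropout".

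On who takes readings, Sections 5.2 and 7 give the task to research assistants or care home staff in Phase 1. Appendix E now admits only homes whose own staff will collect the data. In Phase 2, "Continuing care home residents will continue to receive twice-weekly visits", while people in their own homes measure themselves and have visits on request.

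Elsewhere, dropout means people leaving. Section 7.1 lists electing to drop out as one way Phase 1 visits end, Section 10.12 records type and reason of withdrawal in the CRF and seeks substitutes, and the Section 12.1 tables count dropouts by head.

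**The concern.** The first outcome does not answer its own objective. A participant who stays for the whole study but misses readings raises the figure, and one who leaves may hardly affect it, depending on how the plan is counted after they leave. A commissioner reading a dropout percentage will take it as the share of people lost.

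The denominator is also open. If the plan changes during follow-up, the same readings give different percentages according to which version counts as agreed, and the protocol does not say which one does.

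The second outcome is about what participants are able to do. In care homes, whether a reading is taken depends largely on staff. If residents are frailer and their readings are more complete, pooling them with home participants offsets any fall in adherence with frailty among people who must manage alone. The study ends in service recommendations (Section 12.5), and whether frail people can self-monitor bears directly on those.

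**Working it through.** **1. The protocol's own dropout figures.** The Stage II table in Section 12.1 has 36 leavers of 500, 33 of 464 and 31 of 430.
- Monthly rates: 36/500 = 7.2%, 33/464 = 7.1%, 31/430 = 7.2%. A constant loss of about 7.1% to 7.2% a month reproduces the table to within 2 patients.
- Headcount dropout over three months: (36 + 33 + 31)/500 = 100/500 = 20%.

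**2. The same attrition under the readings definition.** Take equal planned readings each month, so 500 × 3 = 1,500 person-months are planned. Let stayers miss nothing. After month 3, 430 − 31 = 399 remain.
- Leaving at month end: 1 − (500 + 464 + 430)/1,500 = 1 − 1,394/1,500 = 7.1% missing.
- Leaving mid-month: 1 − (482 + 447 + 414.5)/1,500 = 1 − 1,343.5/1,500 = 10.4%.
- Leaving at month start: 1 − (464 + 430 + 399)/1,500 = 1 − 1,293/1,500 = 13.8%.
- If stayers take 80% of readings (assumption), mid-month exit gives 1 − 0.80 × 1,343.5/1,500 = 28.3%.
- Conversely, with no leavers and everyone at 80% of plan, headcount dropout is 0% and the readings shortfall is 20%.

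The two quantities can differ in either direction.

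**3. The denominator (illustration).** A twice-weekly plan over 12 weeks has 24 readings.
- Twelve readings taken: 12/24 = 50% on the fixed plan. If the plan becomes weekly from week 5, it has 8 + 8 = 16 readings, and 12/16 = 75%.
- A participant who takes every reading and leaves at week 6: 12/24 = 50% of the 12-week plan, but 12/12 = 100% of the plan up to exit.

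**4. Pooling staff-taken and self-taken readings.** Let *s* be the care-home share, ρ the correlation in home participants, σ the SD of their adherence, Δf the extra frailty of residents (in SD units), Δa the extra completion in care homes, and τ its SD there. Frailty has SD 1 in both groups, and completion is unrelated to frailty in care homes. Then
- covariance = (1 − s)ρσ + s(1 − s)ΔfΔa
- variance of frailty = 1 + s(1 − s)Δf²
- variance of adherence = (1 − s)σ² + sτ² + s(1 − s)Δa²

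Assumptions not in the protocol: ρ = −0.30, home adherence mean 70% with σ = 20%. Example with s = 0.2, Δf = 1, staff completion 95% (τ = 5%): covariance = 0.8 × (−0.30) × 0.20 + 0.16 × 1 × 0.25 = −0.008; variances 1.16 and 0.0425; r = −0.008/√(1.16 × 0.0425) = −0.04.

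Pooled r by residents' extra frailty:

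| Residents | Staff completion (SD) | 0 SD | 0.5 SD | 1 SD | 1.5 SD |
|---|---|---|---|---|---|
| 100 of 500 | 80% (20%) | −0.24 | −0.19 | −0.15 | −0.10 |
| 100 of 500 | 85% (15%) | −0.24 | −0.18 | −0.11 | −0.05 |
| 100 of 500 | 95% (5%) | −0.23 | −0.13 | −0.04 | +0.05 |
| 400 of 500 | 85% (15%) | −0.07 | 0.00 | +0.06 | +0.12 |
| 400 of 500 | 95% (5%) | −0.08 | +0.06 | +0.18 | +0.29 |

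A simulation that caps adherence at 100%, with staff completion of 96% and 100 residents, gives −0.01 at 1 SD and +0.08 at 1.5 SD.

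The sign changes when sΔfΔa exceeds |ρ|σ = 0.06. With 100 residents of 500, that needs a gap of 0.06/(0.2 × 0.25) = 1.2 SD at 95% completion, or 0.06/(0.2 × 0.15) = 2.0 SD at 85%.

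**The case against.** The strongest reply is that these are secondary, descriptive outcomes of an exploratory study, and that an SAP we have not seen may restrict or stratify the correlation. The protocol never says that staff-taken and self-taken readings will be pooled. The first outcome refers to readings taken by patients, and its reminder split fits app users better than residents. This stands in part: the pooling is inferred from an unrestricted definition. It does not rescue the first outcome. Read literally, the definition leaves residents with almost no numerator, and an SAP would inherit a label that contradicts its measure.

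Four stronger readings are tempting, and the protocol does not support them.
- A reader might infer that schedules are reduced for people who use the devices poorly, so that they look adherent. No section says so. For poor use, Section 7.1 offers extra visits and Section 5.2 describes prompting. What remains is that the agreed version of the plan is not named.
- A reader might infer that the planned attrition of about 7% a month can never be checked. It can, from the withdrawals recorded in the CRF under Section 10.12.
- A reader might infer that the second outcome is also misnamed. It is named adherence and measures adherence. The gap is between that measure and the objective's word, ability.
- A reader might infer that the frailty correlation will reverse. That needs inputs the protocol does not give. Near-complete care-home readings are also not assured, since visits can end at exacerbation (Section 7.1), suspected COVID-19 suspends participation (Appendix E), and hospital admission can end it (Section 10.12).

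**Conclusion.** The point holds, for secondary outcomes only. The mislabelling is explicit in the text: followed as written, the study would report an adherence shortfall under the name of dropout. On the protocol's own attrition, the gap is 20% by headcount against about 7% to 14% of planned readings, if stayers miss none. The denominator is ambiguous because the plan is dynamic.

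For the frailty correlation, the defect is a missing restriction. Pooling weakened the assumed −0.30 in every scenario tried with 100 residents and 400 home participants, mostly to between about −0.25 and −0.01. All of these take staff completion to be higher than self-monitoring adherence. With that split, a sign change appeared only at about 95% staff completion or more with a 1.5 SD frailty gap. It comes much more easily if residents are the majority. Section 5.2 implies at most about 100 continuing residents in Phase 2, but the column order of the Stage II table could be read as 400, so the split is not settled.

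**What to change.** - **Rename and separate.** Call the first outcome adherence. Report dropout as the proportion of enrolled participants who withdraw before their planned end of participation, from the CRF withdrawal record. List ends due to exacerbation, hospital admission or death separately, because a rule that counted everyone stopping before week 12 would treat Phase 1 exacerbations, the event of interest, as dropout. Count substitutes as participants in their own right.
- **Name the denominator.** Compute adherence against the plan in force at each time, with a sensitivity analysis against the plan agreed at the first visit. Using the first-visit plan alone would score system-directed schedule changes as non-adherence.
- **Restrict the correlation.** Compute the frailty–adherence correlation and the two reminder-group percentages in self-monitoring participants. Report care-home completion separately.

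This changes outcome wording and analysis sets, and uses data the protocol already plans to collect. The cost is a smaller sample for the correlation: about 400 if Section 5.2 gives the split, possibly 100 if the Stage II table is read the other way. The protocol should state the intended Phase 2 split so that this loss is known.

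### Sections 5.2 and 7 promise proof of device-condition mappings from a Phase 1 screen that can only be exploratory, and the Phase 2 re-test is not independent of it

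*Protocol*

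**What the plan says.** Secondary outcome 4 (protocol section 6) is described as "Correlation of each type of device for each complication group as a predictor of exacerbation (i.e determine which device(s) are most useful". The synopsis promises the result as a "Table of devices / correlations / confidence levels", and the outcome is evaluated at the end of the study.

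In Phase 1, "all devices will be used to take measurements from all participants" (section 7), with up to 100 care-home residents. Section 5.2 then fixes the consequence for the second phase: "participants will only be asked to use devices that have been proved in" the first. Effectiveness there means yielding relevant data for that person's own conditions. Section 7 repeats that "devices will be allocated to participants based on data gathered in" the first phase, and expects this to show the "best combinations of devices for recording health measurements for different sets of co-morbidities, and prove or disprove the following assumptions". The assumptions that follow are seven complication groups, each with its list of measurements.

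Three other statements bear on the point:
- Sections 7 and 7.1 also let Health Research Assistant (HRA) observations and GP or historical data inform which devices a participant receives.
- Section 5.2 lets Phase 1 participants continue into Phase 2, within its total of 500.
- The closing sentence of section 12.1 describes the study as observational and exploratory, and the lay summary calls it a PoC trial.

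**The concern.** The words *proved* and "prove or disprove the following assumptions" claim more than a many-pair screen in a small group can deliver, and they disagree with the exploratory label in section 12.1. This is more than style, because the same sentences restrict the devices used in Phase 2.

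Two kinds of error matter. A pair that looks good by chance is carried forward with the status of an established fact. A pair that looks poor by chance is dropped for that group and is not measured there again. The end-of-study evaluation can correct the first error, but only partly if people who supplied the selection data also supply the evaluation data. The results feed the interim report to the CCG on device and condition groupings (section 12.2) and, less directly, the service transformation suggestions (section 12.5).

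**Working it through.** The plan gives no figure for this step. The sample-size table in section 12.1 concerns the sensitivity and specificity of the overall algorithm, so there is nothing to reproduce. The check is a count followed by an error calculation.

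**1. Number of pairs (counted from the lists in section 7).**
- Groups: heart failure; COPD/asthma; frailty/falls/syncope; high frailty bedbound; blood disorders/immune suppression; diabetes; renal/liver failure. That is 7.
- Distinct measurements: weight, heart rate, blood pressure, SpO2, CO2, peak flow, respiration rate, temperature, ECG, blood sugar. That is 10, or 9 if the CO2 device is not approved in time.
- All devices are used on all Phase 1 participants, so up to 10 × 7 = 70 pairs can be examined (63 without CO2).
- Pairs named in advance: 5 + 5 + 5 + 6 + 4 + 3 + 4 = 32.

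**2. Assumptions.** A two-sided 5% level per pair, unadjusted, with no device predicting anything. The protocol states no level for these correlations. The only hint is the 1.96 in section 12.1, which belongs to a different calculation.

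**3. Formulas, for m pairs.**
- Expected false positives: 0.05 × m.
- At least one, independent tests: 1 − 0.95^m.
- At least one, common correlation ρ between test statistics: 1 − ∫ φ(u) [Φ((1.96 − √ρ·u)/√(1−ρ)) − Φ((−1.96 − √ρ·u)/√(1−ρ))]^m du, integrated numerically.

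**4. Results.**

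| Pairs | Expected false positives | ρ = 0 | ρ = 0.5 | ρ = 0.8 |
|---|---|---|---|---|
| 70 | 3.5 | 97% | 70% | 33% |
| 63 (no CO2) | 3.15 | 96% | 68% | 32% |
| 32 (pre-listed) | 1.6 | 81% | 52% | 26% |
| 10 (one group) | 0.5 | 40% | 29% | 17% |

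These figures do not depend on the number of participants. The planning table in section 12.1 counts replacements and reaches 184 people cumulatively in the first stage, with 100 under observation at a time. That does not change the table above.

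**5. Independence of the re-test.** Phase 1 has up to 100 participants and Phase 2 has 500 in total, so up to 100/500 = 20% of Phase 2 could be people whose data chose the devices. Section 10.12 says that all data from enrolled participants will be analysed, and nothing in section 6 restricts outcome 4 to new participants.

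**The case against.** The case on the other side is substantial, and much of it stands.

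- *The study is labelled exploratory.* True, in section 12.1, and the lay summary says PoC. A reader might infer that the plan has no exploratory label at all; it has one for the whole study. The narrower point is that outcome 4 and the Phase 1 selection carry proof wording that contradicts it.
- *A multiplicity method may be in an analysis plan that is not shown.* True, and its absence from the protocol is not the finding. The proof wording and the device restriction are in sections 5.2 and 7, where an analysis plan would not change them.
- *No significance rule for selection is stated.* True. The text could equally mean ranking. The percentages describe one plausible rule, not the plan's rule.
- *Chance correlations will not decide allocation alone.* True. HRA observations and GP data also count, so a reader who concludes that chance will determine the devices goes further than the documents.
- *Phase 2 measures the selected devices again.* True. With an independent Phase 2 sample, only about 70 × 0.05 × 0.025 ≈ 0.09 null pairs would be significant in both phases in the same direction. That reassurance needs independence, which continuing participants weaken, and it does nothing for dropped pairs.
- *Seventy is an upper bound.* True. It counts measurements rather than physical devices, liver failure is an exclusion in section 8.2, and a global null is pessimistic for pre-listed pairs. Hence the 32-pair row.

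It is also tempting to divide 100 by 7 and say that only correlations above about 0.53 could reach significance with 14 per group. Group sizes are not given, multimorbid participants fall in several groups, and measurements are repeated twice weekly, so the documents do not support that threshold.

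**Conclusion.** The point holds in limited form. The protocol states a confirmatory claim (devices proved, mappings proved or disproved) that a screen of 32 to 70 pairs in up to 100 residents cannot support, and that contradicts its own exploratory label. It also leaves the selection data free to re-enter the end-of-study evaluation.

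Under the assumed 5% level and no true prediction, 1.6 to 3.5 false leads are expected. The chance of at least one runs from 26% (32 pairs, correlation 0.8) to 97% (70 independent pairs). The width of that range reflects the unknown correlation and the unknown number of pairs. Even the lowest value is about five times the nominal 5%. The wording contradiction and the lack of independence do not rest on these assumptions; only the size does.

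**What to change.** - In sections 5.2 and 7, replace *proved* and *prove or disprove* with wording such as 'selected on exploratory Phase 1 estimates'.
- In section 6 and the synopsis, label secondary outcome 4 exploratory. Report each correlation with its 95% interval and state how many pairs were examined.
- If a confirmatory claim is wanted, limit it to the pairs carried into Phase 2. Test those with a multiplicity adjustment (Holm would do) in Phase 2 participants who were not in Phase 1.

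This needs no extra data. The price is that fewer device-condition pairs can be called proven and that the confirmatory set loses the continuing Phase 1 participants. If all 100 continued, 500 − 100 = 400 would remain before dropout.
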